5.2 Randomisation and Blinding

At the baseline visit (Visit 2), participants will be randomly allocated, in a 1:1:1 ratio to one of the three cohorts. Within the cohort, participants will then be randomly assigned in a 2:1 allocation ratio to receive either EDP1815 or matching placebo treatment.

Interactive response technology (IRT) will be used to administer the randomization schedule centrally. Successfully screened participants will be assigned to the next cohort randomisation number available at the time of their baseline visit to determine their cohort and then to the next treatment randomisation number available within that cohort.

Note that if a participant has withdrawn from treatment within 4 weeks of randomisation and is to be replaced, the next participant to be randomised will automatically be assigned to the same cohort as the participant who was withdrawn instead of being randomly assigned to a cohort. Within the cohort, the replacement participant will be randomly assigned to treatment group with the next within-cohort treatment randomisation number.

The allocation to cohort is not blinded as it is distinguishable to participants and study staff by the number of capsules administered per once-daily dose. The treatment allocation within cohort will be fully blinded to participants, study staff and the sponsor with the exception of the personnel supporting the IRT system, the clinical supplies team, the clinical safety team at [REDACTED], and an unblinded team within [REDACTED] who will produce the interim analysis but have no other involvement in the reporting of the study.

A participant's treatment assignment will not be unblinded for the investigator or study site staff until EOS unless medical treatment of the participant depends on knowing the study treatment the participant received. Participants who are unblinded will be allowed to continue their participation in the study; however, any data collected after the unblinding occurred will be excluded from per-protocol analyses.

For the interim analysis, unblinded aggregate results will be produced by the unblinded team within [REDACTED] and reviewed by EVELO personnel for strategic planning use. These results will not be shared with study site staff, participants, or clinical monitors who will be involved in the collection and review of individual study data.

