7.4.5 Practical Measures to Minimise Bias

Outputs featuring unblinded treatment assignments will be created by the unblinded analysis group within [REDACTED] and shared with selective Evelo personnel who are not directly involved in the conduct of the study.

The members of the unblinded team will not be involved in any aspects of study conduct, including in the development of the final summaries and analyses for the study.

Aggregate data from the unblinded results may be more widely shared, including into the public domain, but no data which may have the potential to unblind will be released beyond the unblinded personnel and DMC. Data with the potential to unblind include:

- Efficacy or safety event data where only participants from one treatment group have experienced the event
- Categorical data where one or more categories contains only participants from one treatment group
- Minimum and maximum values for continuous data
- Time to event data where events at single timepoint occurred in only one treatment group

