- Placebo 10 capsules
- EDP1815 10 capsules
- All Placebo
- All EDP1815
- Total

For concomitant medication, efficacy and safety outputs, columns will be ordered and labelled as follows:

- All Placebo
- EDP1815 1 capsule
- EDP1815 4 capsules
- EDP1815 10 capsules
- All EDP1815 (concomitant medication and safety only)

For the efficacy analyses, if the 3 cohorts of placebo participants are found to be too heterogeneous for pooling, selected efficacy tables will also be presented by treatment within cohort, in which case columns will be ordered and labelled as:

- Placebo 1 capsule
- EDP1815 1 capsule
- Placebo 4 capsules
- EDP1815 4 capsules
- Placebo 10 capsules
- EDP1815 10 capsules

For the primary analysis:

- For study disposition summaries where it is appropriate to report information on participants who failed screening, the enrolled population will be used.
- For safety summaries, the safety population will be used.
- For all other summaries and analyses the mITT population will be used, with selected efficacy outputs reproduced using the per-protocol population.

For the final analysis:

- For partial relapse and complete relapse endpoints analysis Week 16 Responders population will be used.
- For duration endpoints and rebound analysis mITT population will be used.
- For or all other summaries and analyses the Part B population will be used.

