9.1 Pooling of Placebo Cohorts

The assumption that the 3 cohorts of placebo participants can be pooled into a single placebo group to be used as a control for all active doses will be examined using mean (\pm SD) and box plots of percent change in PASI score against time. In addition, a mixed model for repeated measures (MMRM) model will be used to compare the 3 cohorts of placebo participants. The model will include parameters for cohort, visit and baseline PASI score together with cohort*visit and baseline PASI score*visit interactions. LS mean (95% CI) estimates for each placebo cohort will be plotted by visit.

A decision will be made by the Evelo study team, based on examination of the above figures and model, on whether the pooling strategy is appropriate.

If any placebo cohort is considered too different from the other placebo cohorts then no pooling will be used. The pooling of 2 cohorts only will not be considered.

If the pooling strategy is considered appropriate, then the placebo cohorts will be pooled into a single 'all placebo' group for all efficacy analyses and will be used as a common control group for each active EDP1815 treatment group.

If the assumption of similarity across the placebo groups is found to be unreasonable, each placebo dose will be included in the model as a separate dose level and pairwise comparisons between each active EDP1815 dose and placebo will be performed using only the matching placebo dose data from the same cohort.

All efficacy data will be listed, including both individual item scores and calculated questionnaire summary scores.

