9.4.4 Sensitivity Analyses

If the assumption of similarity between the placebo cohorts is supported and placebo cohorts can be pooled, a sensitivity analysis will be performed on the percent change from baseline to Week 16 in PASI score using a Bayesian Emax dose response model on the pooled cohorts in the following form:

$$\text{Response} = E0 + Emax \cdot f(\text{dose})$$

Three possible models will be considered for the $f(\text{dose})$:

- Log-linear: $f(\text{dose}) = \log(\text{dose}+0.01)$, where 0.01 is an offset to allow the model to fit for zero dose (placebo)
- 3-parameter model: $f(\text{dose}) = \text{dose}/(\text{dose}+\text{ED50})$
- 4-parameter model: $f(\text{dose}) = \text{dose}^{\text{slope}}/(\text{dose}^{\text{slope}} + \text{ED50}^{\text{slope}})$

Where:

- Response = Percentage change from baseline in PASI at Week 16
- E0 = the response at dose = 0 (placebo)
- Emax = the maximal response over placebo
- ED50 = the dose that yields 50% of the maximal response
- slope = the dose-response slope parameter

Dose will be fitted as a continuous variable with values of 0, 1, 4 and 10 used to denote the number of active capsules taken by each of the treatment groups.

An inverse gamma prior with shape of 0.001 and scale of 0.001 will be used for the residual variance. Normal, non-informative priors will be used for the E0 and Emax parameters with mean 0 and SD 1000. A functional uniform prior (FUP) will be used, when required, for the ED50 and slope parameters where the prior density of the FUP is based on all the parameters in the model. For the FUP, the density will be calculated for values of dose from 0.01 to 10.01 in steps of 1. The use of a FUP shrinks the dose response towards a flat line throughout the dose range, therefore providing more conservative estimates of the dose-response relationship compared to maximum likelihood ([Bornkamp 2014](#)).

Parameters will be blocked so that the MCMC procedure samples from E0 and Emax first, then the ED50 and slope parameters and finally the residual variance parameter.

100,000 MCMC samples will be generated with a thin of 20 to leave 5000 retained samples after a burn-in of 10,000 samples. The number of samples or thin may be increased to reduce the ratio of the MCSE to the posterior SD, as deemed necessary.

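### Capsule count is open, so the pooled-placebo contrast is only partly blinded; the matched-placebo contrast should be reported whatever the pooling decision

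*SAP*

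**What the plan says.** SAP 5.2 is explicit about what is open and what is blinded. On capsule number: "The allocation to cohort is not blinded as it is distinguishable to participants and study staff". On drug: "The treatment allocation within cohort will be fully blinded to participants, study staff and the sponsor", apart from a few named support teams. Within each cohort, "participants will then be randomly assigned in a 2:1 allocation ratio to receive either EDP1815 or matching placebo treatment". Protocol 5.1 describes the same open cohort allocation, and Protocol 6.1.1 makes PASI a physician-scored measure.

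Pooled placebo is the default comparator: it is named in the estimands (Protocol 7.1.1 and Table 7-1) and in the sample size text (Protocol 7.3, SAP 6). SAP 9.1 has the assumption examined on placebo participants only, using mean and box plots over time and an MMRM with cohort-by-visit terms. Then: "A decision will be made by the Evelo study team, based on examination of the above figures and model, on whether the pooling strategy is" [acceptable]. The rule is all or none, and pooling two cohorts only is ruled out.

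If pooling is accepted, SAP 9.4.3 fits 4 treatment levels and compares each dose with all placebo. The 6-level model with matched contrasts is used only if pooling is rejected. By-cohort tables are conditional in the same way (SAP 8): "if the 3 cohorts of placebo participants are found to be too heterogeneous for pooling, selected efficacy tables will also be presented by treatment within" [each cohort]. SAP 15.2 ties the format of the efficacy outputs, other than the placebo-only ones, to the decision.

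The dose-response model in SAP 9.4.4 is fitted only under pooling: "Dose will be fitted as a continuous variable with values of 0, 1, 4 and 10", where 0 stands for all placebo.

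On access, interim outputs showing treatment are "shared with selective Evelo personnel who are not directly involved in the conduct of the study" (SAP 7.4.5). Data are unblinded for the primary analysis after the Week 20 visit (SAP 5.2).

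**The concern.** Taking ten capsules a day may raise expectations, in the participant and in the physician scoring PASI, more than taking one. Within a cohort both arms share that expectation and it cancels. Against pooled placebo it does not cancel: the 10-capsule arm is compared with a control that mostly took fewer capsules, and the 1-capsule arm with one that mostly took more. An expectation effect that grows with capsule count would then look like a dose response.

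Dose response and optimal dose are secondary objectives, and Protocol 7 says the Bayesian results will guide dose selection. In a study built on estimation, bias in the estimates is the central risk. The plan's protection is the check on placebo heterogeneity. That check rests on small groups, has no stated criterion, and is not tied to a point before active-arm results are available.

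**Working it through.** **Inputs.** From SAP 6: meaningful difference 20 points, SD 25, 5% level (sidedness not stated; two-sided assumed), 15% discontinuation, 42 active and 21 placebo evaluable per cohort. Check: 50 × 0.85 = 42.5 and 25 × 0.85 = 21.25, rounded down. Pooled placebo is 3 × 21 = 63.

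**The plan's own power figures.**
- Pooled: SE = 25 × √(1/42 + 1/63) = 4.98; 20/4.98 = 4.02; power 98.0% (97.8% by noncentral t). The stated figure is above 95%.
- Matched: SE = 25 × √(1/42 + 1/21) = 6.68; 20/6.68 = 2.99; power 84.9% (83.8% by noncentral t). The stated figure is above 80%.

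Both reproduce.

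**Share of the control with a different capsule count.** For any active arm, 42/63 = two thirds of the pooled placebo group.

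**What the heterogeneity check can show.** The SE of the difference between two placebo cohorts is 25 × √(2/21) = 7.72, so the 95% half-width is 1.96 × 7.72 = 15.1 points. A true 10-point difference between two cohorts is detected 25% of the time.

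**Range of assumed gradients.** The documents give no placebo gradient, so this is a scenario range. Let the response shift linearly by 0, −g/2 and −g across the three cohorts, equally in active and placebo, with no drug effect. The pooled placebo mean is −g/2, so the pooled contrast is −g/2 for 10 capsules (towards active), 0 for 4 capsules and +g/2 for 1 capsule (against active). Detection uses a 3-group F test at Week 16 with 2 and 60 df and noncentrality 21 × Σ(mᵢ − m̄)²/625; for g = 10 this is 21 × 50/625 = 1.68. The last column is the chance that the two-sided 95% interval for the pooled 10-capsule contrast excludes 0. For g = 10, 5/4.98 = 1.00 and the chance is 1 − Φ(1.96 − 1.00) + Φ(−1.96 − 1.00) = 17%.

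| Gradient g | Bias, 10 capsules | Bias, 1 capsule | F test detects | 10-capsule interval excludes 0 (nominal 5%) |
|---|---|---|---|---|
| 5 | −2.5 | +2.5 | 8% | 8% |
| 10 | −5 | +5 | 19% | 17% |
| 15 | −7.5 | +7.5 | 38% | 33% |
| 20 | −10 | +10 | 61% | 52% |

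The apparent difference between the 10- and 1-capsule doses equals g. Under the same assumptions, the matched contrast has no bias.

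**Choice of control.** Simulation of 400,000 trials with no drug effect and no gradient gives the chance that at least one of three doses has a 95% interval wholly favouring active:
- always pooled: 6.5%
- always matched: 7.3%
- whichever control is favourable: 10.7%
- control chosen by a placebo-only heterogeneity test at the 5% or 10% level: about 8%

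**The case against.** Several points for the plan stand.

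- Pooling is the stated default, and matched placebo is an all-or-none fallback. The check uses placebo data only, not treatment contrasts.
- A reader might infer that the control group is chosen after unblinding with results in view. The documents do not say so. They give no date for the decision; the inference comes from their silence, from the need to identify placebo participants with their outcomes, and from the absence of any decision point before the Week 20 unblinding.
- A reader might call the pooled contrast not double-blind. That is too strong. Nobody is told active or placebo; the blind is incomplete for this contrast, not absent.
- The 10.7% figure assumes someone who ignores the placebo plots and takes the favourable control. It is an upper bound. A choice that depends only on placebo heterogeneity gives about 8%, and always-matched alone gives 7.3%. The study tests no formal hypothesis, so none of these breaches a stated error rate.
- The gradient is assumed. Nothing in the documents shows its existence, size or direction. The planned check also uses baseline adjustment and every visit, so the Week 16 F test probably understates its sensitivity somewhat.
- A reader might infer that the study team could not take the decision at the interim, because SAP 7.4.5 restricts unblinded outputs. The same section lets aggregate results be shared more widely, and the study team is not defined, so the role is unclear rather than impossible.
- Placebo results by cohort are always tabulated and plotted, and Protocol 7.5 allows summaries by cohort. A reader could form a rough matched difference.

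This limits the criticism but does not answer it. If pooling is accepted, no model-based matched contrast or credible interval is planned, and the check cannot exclude placebo differences approaching the size of the target effect.

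**Conclusion.** The point holds as a gap in reporting and documentation. The open capsule count, the two-thirds mismatch in the pooled control, the coding of all placebo as 0 and the conditional matched contrast are all in the text. The 15-point half-width follows from the plan's own SD and sample size. The bias of 2.5 to 10 points, and the matching detection rates of 8% to 61%, depend on an assumed linear gradient acting equally on active and placebo; they show what the check could miss, not what will happen. The documents do not support a claim that the dose response will be false, or that the control will be picked to suit the result. They support a narrower conclusion: the one contrast that capsule count cannot bias is left out whenever pooling is accepted, and nothing requires that decision to precede sight of active-arm results.

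**What to change.** In SAP 9.1 and 9.4.3:

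(a) Whatever the pooling decision, report the Week 16 matched-placebo contrasts for percentage change in PASI from the 6-level MMRM, with 95% HPD credible intervals, as a sensitivity analysis beside the pooled contrasts. Interpret the dose response with them in view. The dose-response model itself is specified only for pooled placebo, so this asks for no second dose-response fit.

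(b) Either keep pooling fixed as the prespecified main analysis, or have any decision to reject it made and dated on the placebo-only outputs, by people who have not seen active-arm results, before active-arm outputs are released for the primary analysis. The interim unblinded team should not take this decision: SAP 5.2 and 7.4.5 keep that team out of the final analyses and reporting.

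The cost is one run of a model already specified and, if option (b) leaves a decision to be made, a dated record. No extra participants are needed. The matched intervals are wider (SE about 6.7 against 5.0 points; half-width about 13.1 against 9.8), and the report needs a sentence on how to read the two together.

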9.2 Selection of Additional Covariates

The covariates described in [Section 7.2](#) will be considered and included in the primary efficacy model described in [Section 9.4.3](#) for the primary estimand if found to be significant ($p<0.05$). A forward stepwise selection method will be used to include the covariates after the treatment*visit and baseline PASI score*visit interactions have already been fitted.

The covariates selected for this primary model will also be used in all other analytical models including covariates.

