7.6.1 Analysis of Primary Efficacy Endpoint

The assumption that the 3 cohorts of placebo participants can be pooled into a single placebo group to be used as a control for all active doses will be examined using mean ($\pm \text{SD}$) plots and box plots of percent change in PASI score against time. In addition, an MMRM will be used to compare the 3 cohorts of placebo participants. The model will include parameters for cohort, visit and baseline PASI score together with cohort*visit and baseline PASI score*visit interactions. Least squares mean (95% CI) estimates for each placebo cohort will be plotted by visit.

A decision will be made by the Evelo study team, based on examination of the above figures and model, on whether the pooling strategy is appropriate.

The primary analysis will be performed using a Bayesian MMRM. The model will include parameters for treatment*visit and baseline PASI score*visit interactions. Body mass index, gender, country, and time since diagnosis will also be considered and included as parameters if found to be significant ($p < 0.05$). The model will not include an intercept. Visit will consist of 6 levels (Weeks 1, 2, 4, 8, 12, and 16) and treatment will consist of 4 levels (pooled placebo, EDP1815 0.8×10^{11} cells, EDP1815 3.2×10^{11} cells, and EDP1815 8.0×10^{11} cells) if the placebo pooling strategy is considered appropriate or 6 levels (Placebo matching EDP1815 0.8×10^{11} cells, Placebo matching EDP1815 3.2×10^{11} cells, Placebo matching EDP1815 8.0×10^{11} cells, EDP1815 0.8×10^{11} cells, EDP1815 3.2×10^{11} cells, and EDP1815 8.0×10^{11} cells) if the placebo pooling strategy is not considered appropriate.

The priors for all parameters in the model will be non-informative and follow a normal distribution with mean 0 and SD 1000. The prior for the variance-covariance matrix will follow an inverted Wishart distribution with degrees of freedom equal to the number of visits and an identity scale matrix. The choice of Wishart distribution is based on it being the conjugate prior of the inverse-covariance matrix of a multivariate-normal random vector.

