7.2 Covariates and Subgroups

If the placebo groups from the 3 cohorts are found to be too heterogeneous to be pooled (see [Section 9.1](#)), the primary and secondary analyses will be performed using within-cohort comparisons of active and placebo treatments, and summary tables will also be produced by cohort.

Subgroups based on baseline severity of disease and obesity will be defined as follows:

- Using baseline PASI score ($<10, \geq 10$)
- Using baseline PGA score (2, 3)
- Using baseline BMI ($<30 \text{ kg/m}^2, \geq 30 \text{ kg/m}^2$)

For the exploratory analysis indirectly comparing the results from this study to those in the UNVEIL study ([Section 9.6.2](#)) the following subgroup of participants will be used:

- Baseline PGA=3 and Baseline BSA 5-10%

For the inferential models defined in [Section 9](#), in addition to the relevant baseline score where applicable, the following covariates will be considered:

- Body mass index (<30 kg/m², ≥30 kg/m²)
- Sex (male, female)
- Country (UK, Poland, Hungary, USA)
- Time since diagnosis (<2 years, ≥2 years)

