9.4.3 Main Analytical Approach

Percentage change from baseline in PASI score at each visit will be summarised. Mean (+/- SD) percentage change from Baseline over time will be plotted in a figure. Also, waterfall plots will be created to show the ranked individual percentage change from Baseline at Week 16.

The primary analysis will be performed using a Bayesian mixed model for repeated measures (MMRM). The model will include parameters for treatment*visit and baseline PASI score*visit interactions and will not include an intercept.

Treatment will consist of 4 levels (all placebo, EDP1815 1 capsule, EDP1815 4 capsules and EDP1815 10 capsules) if the placebo pooling strategy is considered appropriate or 6 levels (Placebo 1 capsule, Placebo 4 capsules, Placebo 10 capsules, EDP1815 1 capsule, EDP1815 4 capsules, and EDP1815 10

capsules) if the placebo pooling strategy is not considered appropriate. Visit will consist of 7 levels (Weeks 1, 2, 4, 8, 12,16 and 20).

As described in [Section 9.2](#) additional covariates for baseline factors will be assessed using this model for inclusion in all efficacy models.

The priors for all parameters in the model will be non-informative and follow a normal distribution with mean 0 and SD 1000. The prior for the variance-covariance matrix will follow an inverted Wishart distribution with degrees of freedom equal to the number of visits and an identity scale matrix. The choice of Wishart distribution is based on it being the conjugate prior of the inverse-covariance matrix of a multivariate-normal random vector.

The model will be blocked so that the MCMC procedure samples from the treatment*visit parameters first, then the baseline*visit parameters, then any additional fitted covariates and finally the variance-covariance matrix.

100,000 MCMC samples will be generated with a thin of 20 to leave 5000 retained samples after a burn-in of 10,000 samples. The number of samples or thin may be increased to reduce the ratio of the Monte Carlo standard error (MCSE) to the posterior SD, as deemed necessary.

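### Covariates for the primary Bayesian model are chosen by a stepwise p<0.05 rule for which the plan defines no p-value; name them in advance instead

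*SAP*

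**What the plan says.** Protocol 7.6.1 names BMI, gender, country and time since diagnosis, which "will also be considered and included as parameters if found to be significant" at p<0.05. It gives no procedure and no categories. The protocol synopsis says the same.

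SAP 9.2 adds the procedure: "A forward stepwise selection method will be used to include the covariates", once the treatment-by-visit and baseline-PASI-by-visit terms are in the model. It then extends the result: "The covariates selected for this primary model will also be used in all other analytical models including covariates".

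SAP 9.4.3 identifies the model: "The primary analysis will be performed using a Bayesian mixed model for repeated measures (MMRM"), with normal priors and MCMC sampling. It states that "additional covariates for baseline factors will be assessed using this model for inclusion in all efficacy models". Its planned outputs are posterior means, 95% HPD credible intervals and posterior probabilities.

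SAP 7.2 sets the form of the candidates: BMI split at 30 kg/m², sex, country (four levels), and "Time since diagnosis (<2 years, ≥2 years"). SAP 7.5 says that the country effect will be assessed for significance.

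**The concern.** The entry rule needs a p-value, and the model named for the selection does not produce one. No Bayesian equivalent and no frequentist companion model is defined. The only frequentist MMRM on this endpoint is the placebo-only pooling check in SAP 9.1. Nor does the SAP say whether a selected covariate enters as a main effect or by visit. Two competent programmers could arrive at different primary models.

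The choice also spreads:

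- The selected set goes into the secondary models (SAP 9.5.2, 9.5.3.2, 9.5.3.3).
- The interim runs the same primary MMRM (SAP 7.4.3), so interim and final models could hold different covariates.
- The primary model is repeated within BMI subgroups split at 30 (SAP 9.4.5). If dichotomised BMI is selected, it is constant within each subgroup and cannot be estimated there.
- SAP 9.4.3 further allows significant covariates to be removed if model checking shows problems.

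All four covariates are known at baseline, so nothing has to be learned from the outcome. At stake is whether the primary estimate, which guides dose selection, comes from a model fixed in advance.

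**Working it through.** **Inputs.** Difference 20 points, SD 25, 5% level (taken as two-sided), and 42 active and 21 placebo evaluable per cohort (SAP Section 6). That is 63 pooled placebo and 63 + 3×42 = 189 in all. Covariate terms as main effects: BMI 1, sex 1, country 3, time since diagnosis 1, so 6 df. The documents give no R² for the covariates, so every R² below is an assumption.

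**The plan's own power (normal approximation).**
- Pooled: SE = 25×√(1/63+1/42) = 4.98; power = Φ(20/4.98 − 1.96) = 98.0% (stated: above 95%).
- Within cohort: SE = 25×√(1/21+1/42) = 6.68; power = Φ(20/6.68 − 1.96) = 84.9% (stated: above 80%).

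Both statements are reproduced.

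**Worst-case cost of fixing all four.** If all are noise, the expected variance inflation is (N−p−2)/(N−p−q−2), with N=189, p=5 (four treatment levels and baseline PASI) and q=6: 182/176 = 1.034. Power becomes 97.7% pooled and 83.7% within cohort, a loss of about 0.3 and 1.2 points. Both stated bounds still hold.

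**How unstable the selected set is.** The chance that at least one of four noise candidates enters is 1 − 0.95⁴ = 18.5% (18.3% simulated). By a noncentral F calculation with 189 participants and 1 df, a covariate explaining 2% of variance enters 49.8% of the time, and one explaining 3% enters 67.2%. These two figures are for a single-visit test. They illustrate instability and are not derived for the planned seven-visit model.

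**Stepwise against fixed.** Simulated Week 16 ANCOVA, arms 63/42/42/42, no treatment effect, 8,000 runs per row, R² shared equally among the four covariates, with BMI and time since diagnosis acting as continuous variables:

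| Assumed R² | Error, stepwise | Error, fixed two-category | Empirical SE, stepwise | Empirical SE, fixed two-category | Empirical SE, fixed continuous |
|---|---|---|---|---|---|
| 0 | 5.4% | 5.3% | 5.04 | 5.12 | 5.12 |
| 0.1 | 5.2% | 5.1% | 4.89 | 4.83 | 4.78 |
| 0.2 | 5.0% | 4.8% | 4.76 | 4.70 | 4.56 |

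The Monte Carlo error of the error rates is about 0.24 points. Against stepwise, the fixed two-category SE is 1.6% wider, 1.3% narrower and 1.3% narrower. With continuous terms it is 2.3% narrower at R²=0.1 and 4.4% narrower at R²=0.2. A second simulation of 4,000 runs, with two-category covariates and R² again shared equally, gave 1.3% wider at R²=0, 0.7% narrower at 0.05 and 1.9% narrower at 0.10.

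The model-based SE under stepwise averaged 4.98, 4.85 and 4.66 against the empirical 5.04, 4.89 and 4.76, so it is about 1 to 2% too small.

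**Dichotomising.** For a normal covariate cut at upper share s, the information kept is φ(z)²/[s(1−s)]: 64% at 50:50, 62% at 40:60, 49% at 20:80 and 34% at 10:90.

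**BMI derivation.** SAP 5.3.2 multiplies inches by 0.3937 to get cm, where division is needed. Height comes out at 0.3937² = 0.155 of its true value, and BMI is inflated by 1/0.155² ≈ 42-fold for heights recorded in inches.

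**The case against.** The strongest reply is that the freedom is narrow and the harm negligible. The candidates and threshold are in the protocol. The SAP fixes the categories and the fitting order, and uses one set for all models. No formal hypothesis is tested (SAP 7.6). All of this stands, but none of it supplies the missing p-value.

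Three stronger readings are tempting, and the documents do not support them:

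- *Selection inflates false positives or distorts the treatment effect.* The simulated error rates show no material inflation, and entry depends on the covariate's own significance, not on the treatment difference.
- *The plan gives up 2.5 to 5% of precision.* Those figures are 1−√(1−R²) at R² of 5 to 10%. They compare always adjusting with never adjusting and leave out the 6 df. With the 1.034 inflation, the gain over no adjustment is 0.9 to 3.5%, and stepwise selection already captures part of it.
- *The SAP states that selection is done unblinded.* SAP 9.2 does not say so. It is an inference, though a reasonable one: treatment must be fitted first, SAP 5.2 puts the primary analysis after unblinding, and no blinded selection step is described.

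The objection that a fix is not free also stands. The protocol and SAP 7.5 carry the same significance rule. By-visit terms would use up to 6×7 = 42 parameters. SAP 9.5.3.2 already expects low responder numbers, and the SD-1000 priors in SAP 9.5.3.3 do little against separation. The BMI cut matches the obesity subgroup, but that does not require the covariate to take the same form. Continuous BMI would turn the conversion error into extreme leverage points.

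**Conclusion.** The concern holds as one of pre-specification and reproducibility. The primary adjustment set is data-dependent, cannot be reproduced as written, and carries over to the other covariate models. Dichotomising two continuous covariates discards information as well.

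The statistical damage is small: no material change in error rates, model SEs about 1 to 2% too small, and an SE under fixed adjustment that runs from roughly 1% wider (all noise) to about 2% narrower (R² of 10%) than under stepwise, with somewhat more from continuous terms. These sizes rest on assumed R² values and covariate distributions and on a single-visit ANCOVA standing in for the planned MMRM. The absence of a defined test rests on the text alone.

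**What to change.** 1. Delete the stepwise rule in SAP 9.2. Pre-specify BMI and time since diagnosis (both continuous), sex and country as main effects (6 df) in the primary MMRM and the other continuous-endpoint MMRMs.
2. Align SAP 7.5, and record the departure from protocol 7.6.1 and the synopsis in SAP Table 8.
3. For the binary-response models (SAP 9.5.3.2 and 9.5.3.3), state in advance a reduced covariate set to use when responders are sparse.
4. If BMI is kept in two categories, omit it from the models run within BMI subgroups.
5. Correct the inch-to-cm conversion in SAP 5.3.2 before BMI is derived.

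The cost is document wording across these sections. No participants or new data are needed. If all four covariates prove uninformative, power falls by at most about 0.3 points pooled and 1.2 points within cohort.
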